6.1.5 Dosing and Administration

Dose of investigational drug: This trial will include 3–4 dose groups, namely the 0.1 mg, 0.3 mg, 0.5 mg and 0.9 mg dose groups. The dose of protein should be adjusted according to the imaging results of the previous dose group during the trial. The radiation dose for all dose groups at the time of administration should be ranged from 37 to 200MBq.

6.1.6 Route of Administration

Administration method: aspirate [⁶⁸Ga]Ga-NOTA-SNA002 using a syringe and slowly administer by intravenous injection. The injection time should be no less than 1 min. An indwelling needle should be inserted into the subject before intravenous push. followed by extubation after bolus injection of 10 to 20 ml of normal saline, and clinical routine radiation protection treatment was performed on the indwelling needle and syringe. Subjects were instructed to drink no less than 500 mL of water well for hydration multiple times prior to dosing. Subjects should drink and excrete multiple times after dosing to reduce radiation exposure.

6.1.7 Starting Dose and Dose Escalation Schedule

6.1.7.1 Starting Dose

SNA002 does not bind to mouse, rat and dog PD-L1. Therefore, cynomolgus monkey was chosen in biodistribution studies and repeat-dose general toxicity studies. ^{68}Ga -NOTA-SNA002 can specifically bind to PD-L1 proteins of primates, and the radioactivity uptake is low in other organs except for the excretion organs (kidneys and bladder). The estimated absorbed dose (effective dose) converted from cynomolgus monkeys to adult male or female is 0.022-0.023mSv/MBq, which shows good radiation safety. The recommended dose of ^{68}Ga -NOTA-SNA002 for clinical trials is 185 MBq (5mCi), which generates an effective dose of about 4.1 mSv indicating safe use of ^{68}Ga -NOTA-SNA002 for clinical diagnostics. A NOAEL approach based on the pivotal monkey 2-week study toxicity findings was used to determine the maximum recommended starting dose (MRSD) for the first in human study. In the 2-week monkey study, the potential infusion reaction is the only toxicity observed after 3 repeated iv doses. the dose of 1.5 mg/kg (mean $\text{AUC}_{0-t} = 20700 \text{ ng}\cdot\text{h}/\text{mL}$; mean $\text{C}_{\text{max}} = 32000 \text{ ng}/\text{mL}$) and 0.5mg/kg (mean $\text{AUC}_{0-t} = 5060 \text{ ng}\cdot\text{h}/\text{mL}$; mean $\text{C}_{\text{max}} = 10500 \text{ ng}/\text{mL}$) was considered the NOAEL for males and females, respectively. Since the molecular weight of ^{68}Ga -NOTA-SNA002 is less than 100KD, The HED is 0.48 mg/kg (male) and 0.16 mg/kg (female) based on body surface. The MRSD is considered to be 0.048 mg/kg (male) and 0.016 mg/kg (female) (1/10 of NOAEL). The highest dose that nonclinical can cover is considered to be 0.24 mg/kg (male) and 0.08 mg/kg (female) (1/2 of NOAEL). The proposed human dose ranges are from 0.00167 mg/kg (0.1mg flat dose) starting dose to the highest ascending dose 0.01503mg/kg (0.9mg flat dose). The starting dose is 28.74- and 9.58-fold lower than the MRSD for males and females, respectively. The highest ascending 0.01503 mg/kg is covered by nonclinical data ($\frac{1}{2}$ of the NOAEL). Therefore, the proposed clinical mass dose range of 0.00167mg/kg to 0.01503mg/kg is not expected to pose a significant risk to patient safety.

6.1.7.2 Dose Escalation Schedule

The dose escalation is determined through both imaging results and safety results:

Imaging:

The Imaging Reviewer Committee consisted of the principal investigator and nuclear medicine physicians.

- 1) If the first three positive tumor lesions in a certain dose group judged by the IRC having a high image quality (such as $\text{T}/\text{B} > 1.5$, etc.), it can be decided from the imaging perspective to increase to the next dose group after continuing to enroll 3-4 cases in this dose group, or directly increase to the next dose group for further exploration;
→If the quality of the first 3 cases in the subsequent dose group is comparable to that in the previous dose group, the IRC shall discuss whether to discontinue further enrollment from a

imaging perspective (e.g. The image quality of the first 3 cases in the 0.3mg dose group is similar to that in the 0.1mg dose group, then stop recruiting, and the 0.1mg dose was identified as the optimal image dose).

- If the quality of the first 3 cases in the posterior dose group is higher than prior, another 3 to 4 cases will be enrolled. After the completion of the posterior dose group, the IRC will discuss and decide whether this group should not be explored from the imaging aspect (e.g. The image quality of the first 3 cases in the 0.3mg dose group is higher than that in the 0.1mg dose group, then 3-4 cases , and the subsequent dose exploration was not carried out, and the 0.3mg dose was identified as the optimal image dose).

- 2) If the first three positive tumor lesions in a certain dose group judged by IRC present poor imaging quality (such as $T/B \leq 1$) or nonvisualization (functional imaging without nuclides), the decision of stopping enroll in this dose group can be made from an imaging perspective, and the dose group can directly increase to the next or second dose group (for example, if the imaging quality of the 0.1mg dose group is poor in three consecutive cases, the dose group can increase to the 0.3mg or 0.5mg dose group);
- 3) If the last dose group shows nonvisualization of the positive tumor lesions determined by the IRC in the first three cases, discussion will be conducted to determine whether to adjust the subsequent dose from the imaging perspective or terminate the entire clinical trial.
- 4) After the dose escalation of all dose groups is completed, the imaging expert committee and the principal investigator will decide whether to continue enrolling 3-4 subjects in a certain initially identified optimal dose group for further exploration.

Security:

The principal investigator determines whether to increase the dose from the perspective of safety. Dose escalation should be stopped if one of the principles happen:① at least half of subjects in a dose group experience CTCAE grade 2 (or moderate) or above adverse reactions;② or at least 1/3 subjects experience CTCAE grade 3 (or severe) or above adverse reactions;③ or one serious adverse reaction in certain group.

The dose escalation will be determined by the principal investigator based on both imaging and safety results. During the clinical trial, based on the principle of subject protection, the dose group can be rapidly escalated to the subsequent dose group if nonvisualization or the above safety events happens after only one subject enrolled according to the investigator's discretion.

[figure not shown]

Figure 3 Dose escalation

After the dose escalation of all dose groups is completed, the imaging expert committee and the principal investigator will decide whether to enroll another 3 or 4 patients in the identified optimal dose group.

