	
the imaging schedule may be modified based on the imaging data from the first cohort of patients.
 
The optimal time point for PET scanning will be determined based on the analysis of the tumor to background ratio and tumor to blood pool ratio at different timepoints. Tumor to background ratio is defined as the ratio between tumor tracer uptake and the radioactivity on the opposite site or gluteus maximus, etc. The first PET scan will be performed in combination with a low-dose CT scan for attenuation correction and anatomic reference. An independent radiology review committee (IRC), consisting of principal investigator and nuclear medicine physicians, will be established to evaluate all imaging data.
 
If there is no radioactivity or a small amount of radioactivity in the target lesion as evaluated by the IRC, and the safety criteria are met, the dose will be escalated per the escalation guidelines. If the tumor to background ratio is high per the IRC, three patients will be enrolled at the next higher level and the IRC will determine whether dose escalation should stop based on the imaging data from these three patients. Blood samples will be collected from a peripheral vein to evaluate ADA, PK and the radioactivity in the circulation.
 
 • The time points for blood sample collection are as follows: within 30 minutes before injection of SNA002, at 2 ± 1 minutes, 5 ± 1 minutes, 10 ± 1 minutes, 30 ± 2 minutes, 50 ± 5 minutes, 100 ± 5 minutes and 150 ± 10 minutes post injection. All blood samples are sent to the central laboratory for PK analysis. Radioactivity in the blood sample (whole blood and serum) will be obtained using a γ-well-type detector and measured activity concentrations will be converted to percentage injected activity/L. • Urine sample will be collected to evaluate the renal excretion of radioactivity before injection, at 90 ± 30 minutes, 180 ± 30 minutes and 300 ± 30 minutes post injection. Counts in aliquots of serum or urine will be obtained using a γ-well-type detector and measured activity concentrations will be converted to percentage injected activity/L. 
Blood samples will be taken 30 minutes before administration, on $D6\pm 1$d and $D28\pm 2$d, and will be sent to the central laboratory for ADA analysis. Patients were discharged from the study after blood samples were collected on $D28\pm 2$d. Following the last PET scan, tumor biopsies or operation (if surgery is available) will be obtained. The investigator will determine the number and location of lesions for biopsy for each patient in consultation with the surgeon or interventional radiologist; these should be easily accessible and have positive or negative tracer uptake. Biopsy sites should not exceed 5 for each patient and ideally include both negative lesions and positive lesions. If taken an operation on tumor, the IRC will observe IHC result of tumor and PET scan.
 
The study will be end for patient after completing blood collection on $D28\pm 2$d.
 
Region-of-Interest Definition
 
Regions of interest (ROIs) will be used to determined SNA002 uptake in different organs. Organs with tracer uptake will be drawn using PMOD software based on the PET image, including all activities on the PET images that are contributing to the organ. For organs without tracer uptake, organ delineation will be based on CT data.
 
To calculate the biodistribution and dosimetry in normal organs with tracer uptake, a semiautomatic (region grow) method will be used to delineate the ROI on the PET images. For normal organs without tracer uptake, the ROI will be delineated based on CT scan.
 
Dosimetry
 
Time-activity curves were derived from volumes of interest for each source organ (i.e., brain, heart, lungs, liver, spleen, kidneys, and thyroid) delineated on the whole-body images using PMOD.
 
To define volumes of interest (VOIs) the dynamic study was loaded with all or some frames averaged, depending on the evaluated organ. VOIs were defined manually for heart, liver, gallbladder, kidneys with all frames averaged.
 
Using the PMOD software the VOIs consisted of regions of interest (ROIs) which were defined at the outer contour of the organ. In this way (decay-corrected) TACs of the organs' average radioactivity concentrations and their volumes were obtained.
 
An example, FYI: Source Organs: For dosimetric calculations, the following source organs were included: kidneys, red marrow, cortical bone mineral surface, trabecular bone mineral surface, urinary bladder content, and remainder body. Red marrow activity uptake was estimated from venous blood sampling.
				

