5.4 Premature Termination or Suspension of Study

According to CTCAE (5.0), the clinical trial should be terminated if over one half of the subjects have grade 2 or greater investigational drug-related AEs or if one case of investigational drug-related SAE is observed.

- Major errors are identified in the clinical trial protocol during the trial, which render drug evaluation difficult.
- Termination requested by the sponsor under the premise that the interests and safety of the subjects are fully guaranteed.
- Trial termination ordered by the NMPA or Ethics Committee due to some tests.
- Inability to recruit patients.
- Lack of imaging even after dose adjustment.

Regardless of whether the trial is terminated by the sponsor or the investigator,

- The investigator should return all investigational drugs, eCRF and relevant trial materials to

the sponsor.

- The sponsor or the investigator should provide a written statement on the reason for early trial termination and inform all principal investigators related to this trial, the Ethics Committee, and NMPA as soon as possible. In addition, all subjects should be informed of the termination of the trial.

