10.5 Determination of Sample Size

This is an exploratory study and sample size determination is not based on any hypothesis testing. SNA002 is a ⁶⁸Ga-labeled radiodiagnostic reagent that has no pharmacological or toxicological effects during clinical use. Based on the sample size for ⁶⁸Ga-NOTA-2Rs15d (a total of 20 subjects, with 5–7 subjects per group) and ⁸⁹Zr-Df-IAB22M2C (a total of 6 subjects, with 1 subject per group), 12–28 subjects are intended to be enrolled in this trial. Each group is planned to include 3 to 7 subjects, and the number of subjects will be adjusted based on the imaging results. The detailed rules for adjustment are shown in the “General considerations for dose escalation” section. A total of 12–28 subjects will be enrolled into the effective dose group to allow sufficient observation of preliminary safety and common adverse reactions.

11 Source Documents and Access To Source Data/Documents

Source documents are defined as original documents recording observation results and clinical study activities. Source documents include but are not confined to the following: progress notes, electronic data, screening log, and data recorded by automated instruments. For more details, please refer to the source document list. The investigators should maintain all source documents related to the clinical trial. These source documents will be submitted to the authorized staff (see below) for direct review as per ICF:

- Clinical trial team and authorized staff
- Sponsor and its authorized agent
- Ethics committee
- The supervisory bodies and other staff from governmental agencies who are responsible for safeguarding the safety of the subjects

Direct review consists of the inspection, analysis, verification and reproduction of records and reports which are of great significance for evaluating the clinical trial by the supervisory bodies.

The source document list can be found in the source document list table.

12 Quality Assurance and Quality Control

- Quality control measures of the laboratory : The laboratory should provide documents such as quality control certificate.
- Investigators participating in the clinical trial must have the professional skills, qualifications, and competence related to clinical trials. They must pass the qualification examinations. Minimum mobility of the investigators is required during the clinical trial.

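### The rapid-escalation clause permits a higher dose after the safety events that should stop escalation, and one non-serious grade 3 reaction in three subjects triggers no required review before more subjects get that dose

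*Combined protocol and SAP*

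**What the plan says.** The Security part of section 6.1.7.2, repeated in the Protocol Summary, lists three criteria for a dose group:

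- Criterion 1: at least half of subjects with a reaction of grade 2 or above.
- Criterion 2: at least one third with a reaction of grade 3 or above.
- Criterion 3: one serious reaction.

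The consequence is "Dose escalation should be stopped if one of the principles happen". The paragraph opens with "The principal investigator determines whether to increase the dose from the perspective of safety", and the Study Design text of the Protocol Summary links safety to the same step: "and the safety criteria are met, the dose will be escalated per the escalation guidelines".

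The rapid-escalation clause follows. At the investigator's discretion, "the dose group can be rapidly escalated to the subsequent dose group if nonvisualization or the above safety events happens after only one subject".

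Enrolment at the same dose is governed by image quality. Under imaging rule 1, adding 3 to 4 cases after good images is optional. For a later group whose images are better than the previous group's, the wording is firmer: if quality is "higher than prior, another 3 to 4 cases will be enrolled". Section 10.5 agrees: "Each group is planned to include 3 to 7 subjects, and the number of subjects will be adjusted based on the imaging results".

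Two other rules stop dosing. Section 5.4 terminates the trial if "over one half of the subjects have grade 2 or greater investigational drug-related AEs", or after one drug-related SAE. Section 8.5 halts administration at three grade 2 events judged probably related. Section 8.6 names a safety committee but gives it no trigger.

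**The concern.** The stop rule and the rapid-escalation clause give opposite instructions for the same event. An investigator who sees a grade 3 reaction in the first subject of a group must stop escalating under one sentence and may escalate under another. In a first-in-human study with safety as a primary objective, the permissive sentence should not be there.

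The criteria also say nothing about further enrolment at the dose where the reaction occurred. If neither 5.4 nor 8.5 applies, 3 to 4 more patients can receive a dose that has met the protocol's own safety criterion, because the images were good, without anyone being required to review the event first.

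**Working it through.** **Planned size.** Four dose groups of 3 to 7 give 4 × 3 = 12 and 4 × 7 = 28, matching the 12 to 28 in section 10.5. Three subjects plus a fill-in of 3 to 4 give 6 to 7 per group.

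**Rapid-escalation clause, one subject treated.**

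- Grade 2 reaction: 1/1 ≥ 1/2, so criterion 1 is met.
- Grade 3 reaction: 1/1 ≥ 1/2 and 1/1 ≥ 1/3, so criteria 1 and 2 are met.
- Section 5.4 in the first cohort: 1/1 is over one half, so the trial terminates.
- Section 5.4 in a later cohort: the denominator is not defined. Read trial-wide after three event-free subjects, 1/(3 + 1) = 25% and the rule does not fire. Read per group, it does.
- A drug-related SAE terminates the trial under 5.4 in any cohort.

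Every safety event that could activate the clause also meets the stop rule.

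**Fill-in decision, first three subjects.** Reactions are taken as drug-related and non-serious, one per subject, and earlier cohorts as event-free groups of three.

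| Pattern | Criterion 1 | Criterion 2 | 5.4, first cohort | 5.4, later, trial-wide | 8.5 |
|---|---|---|---|---|---|
| One grade 3 | 1/3, no | 1/3, yes | 1/3, no | 1/6, 1/9, 1/12, no | at most 1 event, no |
| Two grade 2 | 2/3, yes | 0/3, no | 2/3, yes | 2/6, 2/9, 2/12, no | 2 events, no |
| One grade 3, one grade 2 | 2/3, yes | 1/3, yes | 2/3, yes | 2/6, 2/9, 2/12, no | at most 2 events, no |
| Three grade 2 | 3/3, yes | 0/3, no | 3/3, yes | 3/6, 3/9, 3/12, no | 3 events, yes if probably related |

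Read per group, 5.4 fires in rows two to four in every cohort. Only row one escapes 5.4 on both readings. It does not depend on clean earlier cohorts for 5.4: if the earlier subjects together were at or below one half, adding a group at 1/3 cannot take the total above one half. It does require that earlier events do not bring the 8.5 count to three.

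Row one can occur. Section 8.2.1 counts restricted self-care as severe, and section 8.1.2 does not list it as a criterion for seriousness.

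**Size.** No reaction rate is given for SNA002. Sections 2.1.1 to 2.1.3 describe three other tracers with 22 + 13 + 16 = 51 patients and no drug-related event of grade 3 or above. The one-sided 95% upper bound is 1 − 0.05^(1/51) = 5.7%, for different agents. For an assumed rate p of grade 3 or above:

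| p | Exactly one of three, 3p(1 − p)² | Expected further reactors in fill-in, 3p to 4p |
|---|---|---|
| 1% | 2.9% | 0.03 to 0.04 |
| 3% | 8.5% | 0.09 to 0.12 |
| 5% | 13.5% | 0.15 to 0.20 |

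The middle column overstates row one somewhat. It includes serious reactions, which 5.4 covers, and groups in which another subject has a grade 2 reaction.

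**The case against.** Figure 3 is the decision diagram for these rules and is not visible, so it may show a safety hold. Section 6.1.7.2 says that escalation rests on imaging and safety together and gives the decision to the principal investigator, who also sits on the imaging committee and could decline the fill-in. Fill-in is mostly optional. Treating three more subjects at the same dose after one reaction in three is ordinary 3+3 practice. Many severe events involve hospitalization or disability and would be serious. Exposure is a single dose, and the highest planned dose is below both calculated maximum starting doses. The rapid-escalation clause is discretionary and is introduced as a measure to protect subjects.

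Most of this stands and limits the second gap to a missing review step: adding subjects at that dose is not itself a fault. It does not rescue the clause, whose stated purpose is at odds with moving to a higher dose after a reaction.

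Three stronger readings are tempting but unsupported:

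- A reader might infer that criterion 1 is unprotected in general. In the first cohort of three it always meets 5.4. Later it is a gap only if 5.4 is read trial-wide and fewer than three 8.5 events have occurred.
- A reader might infer that event-free additions, taking 1/3 to 1/6 or 1/7, lift the stop. Nothing says that the fraction is reassessed.
- A reader might infer that such a dose would be recommended. The imaging rules name an optimal image dose, and section 10.4.2 judges optimal dosage on imaging. Neither says that this alone fixes the recommended diagnostic dose.

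**Conclusion.** The contradiction between the stop rule and the rapid-escalation clause is plain in both places where they appear. In the first cohort 5.4 would override it. In later cohorts it is a live conflict for a non-serious reaction if 5.4 is read trial-wide.

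The review gap is firm for one pattern only: exactly one non-serious grade 3 reaction in the first three, with no other reaction of grade 2 or above and an 8.5 count below three. Fill-in is worded as mandatory only for a later group with better images. Criterion 1, and criterion 2 with more than one subject affected at grade 2 or above, share the gap only under the conditions above.

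Absolute risk is probably low; the rates behind that judgement are assumed, not taken from the documents. The conclusion on fill-in is subject to Figure 3.

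**What to change.** In section 6.1.7.2 and the Protocol Summary:

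1. Delete the safety-event alternative from the rapid-escalation clause, so that it covers nonvisualization only.
2. Add: *If safety criterion 1 or 2 is met at a dose, no further subject is enrolled at that dose until the section 8.6 safety committee has reviewed the events.*

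Adding subjects at that dose after the review remains allowed. Section 8.6 needs a line on how the committee receives such a referral, because 8.5 currently sends events to the imaging committee. Align Figure 3 if needed.

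The cost is one deletion and one sentence in each of two places, plus that line. No new data or thresholds are needed. The downside is that a single grade 3 reaction in three subjects may briefly pause a dose group.

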8.5 Study Halting Rules

Administration of study agent will be halted when three grade 2 AEs determined to be “probably related” are reported to the IRC. The IRC will notify the study sponsor and investigators immediately when the third grade 2 event is reported, and enrollment screens will stop accepting new study participants.

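### Section 6.1.7.2 allows rapid escalation after one subject on the same safety events that it says should stop escalation

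*Combined protocol and SAP*

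**What the plan says.** The safety part of 6.1.7.2 (headed Security) states: "Dose escalation should be stopped if one of the principles happen". Three criteria follow:

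1. half or more of a dose group with reactions of grade 2 or worse;
2. a third or more with reactions of grade 3 or worse;
3. one serious adverse reaction in a group.

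The next paragraph, citing subject protection, says: "the dose group can be rapidly escalated to the subsequent dose group if nonvisualization or the above safety events happens". This applies with a single subject enrolled and is left to the investigator's discretion. The protocol summary carries the same pair of statements in nearly the same words.

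Three other places bear on this:

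- **Protocol summary, Study Design.** Where lesion uptake is absent or low, "and the safety criteria are met, the dose will be escalated per the escalation guidelines".
- **Section 5.4.** One ground for ending the trial is how many subjects are affected: "the clinical trial should be terminated if over one half of the subjects have grade 2 or greater investigational drug-related AEs". The second ground in the same sentence is a single event: "or if one case of investigational drug-related SAE is observed".
- **Section 8.5.** The rule concerns events rated probably related and reported to the imaging review committee. It begins: "Administration of study agent will be halted when three grade 2 AEs determined to be".

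The planned protein doses in 6.1.5 are "namely the 0.1 mg, 0.3 mg, 0.5 mg and 0.9 mg dose groups". On radioactivity, the same section says: "The radiation dose for all dose groups at the time of administration should be ranged from 37 to 200MBq".

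**The concern.** Rapid escalation after one subject makes sense for nonvisualization, because further subjects at a dose that gives no image would be exposed for no benefit. It does not make sense as a response to harm. The paragraph nevertheless names safety events as a second trigger, and the only safety events it can refer to are the three stop criteria just above it.

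Safety and tolerability is the first primary objective, and this is a first-in-human study. An investigator who gave the next subject a higher protein dose after a grade 2 or worse reaction would be acting within the text, although the preceding paragraph says escalation should stop. The protocol names infusion-related reactions as the main expected safety risk, and a potential infusion reaction was the only toxicity seen in the monkey study.

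**Working it through.** There is no sample size or power figure to reproduce, because section 10.2 sets no hypothesis test. The check applies each rule to the same event and sees which action follows.

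**Step 1: the stop criteria at one subject.** One grade 2 or worse reaction gives 1/1 = 100%, against a threshold of 50%. One grade 3 or worse reaction gives 100%, against 33%. One serious reaction meets criterion 3 directly. Any such event in a group's first subject therefore meets a stop criterion and the rapid-escalation condition together.

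**Step 2: what section 5.4 already covers.** It ends the trial on one drug-related SAE, so serious reactions are covered in every group. It also ends the trial when more than half of subjects have grade 2 or greater drug-related AEs, but it does not say whether this is counted per group or across the trial.

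- Trial's first subject (0.1 mg): 1/1, over one half on either count. Covered.
- First subject of a later group, counted per group: 1/1. Covered.
- First subject of a later group, counted across the trial, with *n* earlier subjects and no earlier reaction: the share is 1/(*n* + 1).

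| Group | Earlier subjects *n* | Share with a reaction | Over one half? |
|---|---|---|---|
| 0.3 mg | 1 | 1/2 = 0.50 | No |
| 0.3 mg | 3 | 1/4 = 0.25 | No |
| 0.3 mg | 7 | 1/8 = 0.125 | No |
| 0.5 mg | 6 | 1/7 = 0.143 | No |
| 0.5 mg | 14 | 1/15 = 0.067 | No |

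The rows with 3 and 7, and with 6 and 14, use the planned 3 to 7 subjects per group. The row with 1 is the extreme case of moving up after a single 0.1 mg subject. On the trial-wide count, 5.4 does not stop any of these.

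**Step 3: section 8.5.** It acts at the third grade 2 event judged probably related, so one event does not trigger it.

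**Step 4: the remaining gap.** What is left is a non-serious reaction of grade 2 or worse in the first subject at 0.3 or 0.5 mg. The 0.9 mg group is left out because no higher dose is planned. The gap can include grade 3: section 8.2.1 counts restricted daily self-care as severe, and that alone does not meet the SAE definition in 8.1.2.

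**Step 5: size of the dose step.** 0.5/0.3 = 1.67 and 0.9/0.5 = 1.80. The radioactivity range is 37 to 200 MBq in every group.

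**Step 6: how often the rules could collide (illustrative).** The documents give no reaction rate. Assume that both the 0.3 and 0.5 mg groups open and that each first subject has the same independent chance *p* of a grade 2 or worse reaction. The chance of at least one collision is 1 − (1 − *p*)²:

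- *p* = 0.05: 1 − 0.95² = 0.0975, about 10%
- *p* = 0.10: 1 − 0.90² = 0.19, or 19%
- *p* = 0.20: 1 − 0.80² = 0.36, or 36%

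This is the chance that the two rules conflict, not the chance that anyone is escalated.

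**The case against.** The strongest reply is that the conflict has little practical effect. The clause is permissive, while the stop rule and 5.4 both say what should happen. The principal investigator decides on imaging and safety results together, and 8.6 provides a safety committee. The stated purpose of subject protection suggests a drafting or translation slip. The risk is low: the protocol calls infusion-related reactions medically manageable, the radioactivity range is unchanged, and the top dose of 0.01503 mg/kg is below the maximum recommended starting dose (0.016 mg/kg for females, 0.048 mg/kg for males). All of this stands and limits the consequence. None of it says which paragraph governs, and a probable slip is a reason to correct the text.

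Three narrower points also have some force:

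- **Precedence.** If *should* overrides *can* for 5.4, it ought to do so for the stop rule as well, and no gap remains. On that reading the safety trigger could never operate and should still be deleted. On the opposite reading, 5.4 bars nothing and the gap is wider than described here. The documents do not choose.
- **Denominator.** Assessed on a completed group of 3 to 7, one grade 2 reaction is 1/3 to 1/7, below one half. But the rapid-escalation sentence itself reads the safety events at one subject, so the 1/1 reading comes from the protocol.
- **The summary's safety condition.** It is attached to the low-uptake branch and is not worded as an exclusive rule. It shows intent and no more.

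Figure 3 is not shown in the available text and could not be checked.

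**Conclusion.** The rule is wrong as written, in both 6.1.7.2 and the protocol summary: one event meets a stop criterion and also a permission to escalate, and no text states which prevails. This does not depend on any assumed reaction rate.

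The extent of the practical gap does depend on reading. If 5.4 is binding and counted across the trial, with no earlier reactions, the gap is a non-serious grade 2 or worse reaction in the first subject at 0.3 or 0.5 mg, followed by a 1.67- or 1.8-fold higher protein dose. If 5.4 is counted per group, it closes the gap. The 10% to 36% collision figures are illustrative and carry no weight in the conclusion.

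The expected harm is limited, but the sentence must be corrected because it undercuts a first-in-human safety stop.

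**What to change.** In the rapid-escalation sentence of 6.1.7.2 and its copy in the protocol summary, delete the safety events as a trigger and add a condition. The sentence should then say that the investigator may move to the next dose group after one subject if nonvisualization occurs and none of safety criteria 1 to 3 is met. Leave the stop rule itself unchanged.

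The cost is a wording change in two places, with no added patients or procedures. The investigator loses a little discretion: this sentence could no longer be used to move up after a safety event in a group's first subject. The criteria are read at one subject only to decide on rapid escalation, so the change creates no new stop and does not alter when the existing stop rule is assessed.

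It would also help to state whether 5.4 counts per group or across the trial, and that the stop rule, 5.4 and 8.5 take precedence over rapid escalation. The correction does not depend on either.
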